8.1 Investigator’s Responsibilities

Investigators are responsible for monitoring the safety of subjects who have entered this study and for assuring appropriate medical care is provided. In addition, investigators are responsible for alerting BNI or its designee to any event that seems unusual, even if the event may be considered an unanticipated benefit to the subject, and for reporting the event on the appropriate CRF or safety report form.

Investigators are responsible for providing subjects who experience adverse events, especially SAEs that cause subjects to discontinue participation in the study, with appropriate medical care. Frequency of follow-up of any particular adverse event is left to the discretion of the investigator. Duration of follow-up and requirement for immediate SAE reporting (within 24 hours of becoming aware of the event) are described below.

8.2 Definition of Adverse Events (AE)

An AE is any untoward (unfavorable, harmful, or pathologic) medical occurrence in a subject administered a pharmaceutical (investigational) product even if the event does not necessarily have a causal relationship with this treatment. An AE can therefore be any unfavorable and unintended sign (including an abnormal laboratory finding), symptom, or disease temporally associated with the use of a medicinal (investigational) product whether or not related to the medicinal (investigational) product (ICH E2A II/A/1, 21 CFR 312.32).

For the purpose of this clinical study, adverse events include only treatment-emergent events which are either new or represent detectable exacerbations of pre-existing conditions. Adverse events may include, but are not limited to:

1. Subjective or objective symptoms spontaneously offered by the subject and/or observed by the Investigator or study staff including laboratory abnormalities of clinical significance. Any adverse events experienced by the subject through the completion of final study procedures.
2. AEs not previously observed in the subject that emerge during the protocol-specific AE reporting period, including signs or symptoms associated with metastatic castration-resistant prostate cancer that were not present before the AE reporting period
3. Complications that occur as a result of protocol-mandated interventions

For the purposes of this study, the following exceptions to the definitions above will **NOT** be considered an Adverse Event:

Pre-existing condition: A pre-existing condition (documented on the medical history CRF) is not considered an AE unless the severity, frequency, or character of the event worsens during the study period.

Preplanned hospitalization: A hospitalization planned before signing the informed consent form is not considered an SAE, but rather a therapeutic intervention. However, if during the pre-planned hospitalization an event occurs, which prolongs the hospitalization or meets any other SAE criteria, the event will be considered an SAE. Surgeries or interventions that were under consideration, but not performed before enrollment in the study will not be considered serious if they are performed after enrollment in the study for a condition that has not changed from its baseline level. Hospitalizations for social reasons or due to long travel distances are also not SAEs. Diagnostic testing and procedures: Testing and procedures should not be reported as adverse events or serious adverse events, but rather the cause for the test or procedure should be reported.

8.3 Definition of Expected and Unexpected Events

8.3.1 Expected Events

Expected events are those that have been previously identified as resulting from administration of the investigational product. For the purpose of this study, an adverse event is considered expected when it appears in the current adverse event list, the Investigator's Brochure, the package insert or is included in the informed consent document as a potential risk. An event will be considered expected if the event is thought to be related to a study procedure, and the event occurs with reasonable frequency and similar intensity in the day-to-day care of a patient with prostate cancer treated with GnRH agonists or bisphosphonates. Examples of adverse events that are expected during the course of treatment for prostate cancer with GnRH agonists include, but are not limited to malaise/fatigue, hot flashes/sweating, gynecomastia, testicular atrophy or pain, impotence, and clinically significant and non-significant alterations in laboratory parameters including transient increases in testosterone levels. For subjects taking bisphosphonates (e.g., Zometa), expected events would include flu-like symptoms (fever, chills, myalgia, fatigue), injection site redness, swelling, and pain (for injection or infusion-delivered bisphosphonates); joint and/or muscle pain; osteonecrosis of the jaw, and renal insufficiency. Expected events associated with GM-CSF (at therapeutic doses) include mild to moderate headache, fever, arthralgia, chills, and myalgia. Injection site reactions such as pain, redness, swelling, induration, and pruritus, or systemic injection reactions such as fever $\geq 104^{\circ}\text{F}$; myalgia, headache, nausea, fatigue lasting less than 72 hours are expected events for PROSTVAC-V/F.

If, however, the investigator considers an expected event to be unexpectedly severe or more frequent than usual for a patient with prostate cancer treated with GnRH agonists/antagonists, GM-CSF, or bisphosphonates, the event will be captured on the AE CRF (see below). Similarly, if the event is

associated with PROSTVAC-V/F, and is unexpectedly severe, such as a dose-limiting toxicity, it will also be recorded on the AE CRF.

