5.2 Dose-limiting Toxicities and Trial Stopping Rules

5.2.1 Dose-limiting Toxicities

For the purposes of this trial, a dose-limiting toxicity (DLT) is defined as any anaphylactic reaction, a full-thickness ulceration/necrosis, or any AE \geq Grade 3 definitely related to study drug with the following exceptions:

- Local injection site reactions lasting < 72 hours: pain, redness, swelling, induration, or pruritus
- Systemic injection reactions lasting < 72 hours: fever; myalgia, headache, nausea, fatigue

Study drug should be discontinued for the subject in the case of a definitely related anaphylactic reaction or full-thickness ulceration/necrosis. Re-exposure to study drug after development of other related AE \geq Grade 3 should only occur if the event resolved or is reduced to grade 1 toxicity.

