8.3.2 Unexpected Events

Unexpected events are those considered unexpected when it varies in nature, intensity or frequency from the information provided in the current adverse event list, the Investigator's Brochure, the package insert or when it is not included the informed consent document as a potential risk. An event will be considered to be *unexpected* for GnRH agonist/antagonist, GM-CSF, or bisphosphonate therapy or a study procedure if it is not identified in the package insert, or is unexpectedly more severe or more frequent than events described in the package insert, or is related to PROSTVAC-V/F (with the exceptions for injection site and systemic reactions as noted above).

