8.4 Collecting and Recording Adverse Events

The Investigator will monitor the occurrence of adverse event for each subject during the course of the study. All AEs (as defined above) reported by the subject, observed by the Investigator, or documented in medical records will be listed on the AE CRF, whether believed by the Investigator to be related or unrelated to the study vaccine.

All AEs must be reviewed, graded and causality determined by an Investigator listed on the form FDA 1572 at the research center reporting the event(s). Collection of adverse events begins at the time the subject signs informed consent and continues for 28 days following administration of the last dose of study medication.

Adverse event terms should be recorded concisely, using acceptable medical terms. When possible, a diagnosis (*i.e.*, disease or syndrome) rather than the component signs and symptoms should be recorded on the CRF (*e.g.*, congestive heart failure rather than dyspnea, rales, and cyanosis). However, signs and symptoms considered unrelated to syndromes or diseases are to be recorded as individual adverse events on the CRF (*e.g.*, if congestive heart failure and severe headache are observed at the same time, each event is to be recorded as an individual adverse event). Only abnormal laboratory values that result in clinical sequelae or require medication for treatment should be recorded as an adverse event. The adverse event should not be recorded as a procedure or clinical measurement (*i.e.*, a laboratory or vital sign). The underlying reason for the procedure or the abnormal clinical measurements, and, whenever possible, a diagnosis, should be recorded. The diagnosis should be recorded; not the individual lab test name.

Death is considered to be an outcome of an adverse event. The cause of death should be recorded on the AE CRF (*e.g.*, congestive heart failure with an outcome of death rather than the term "death").

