9.1.1. Incidence of Adverse Events

The frequency and percentage of subjects with TEAEs will be tabulated for overall incidence by system organ class (SOC) and PT for primary period TEAEs, booster period TEAEs and overall.

TEAEs will also be summarized by treatment arm and overall for the highest CTCAE grade and highest relationship to study treatment within each subject. Related TEAEs, serious TEAEs, related serious TEAEs, and TEAEs resulting in study product discontinuation will be similarly summarized. Additionally, the incidence of TEAEs and related TEAEs will be summarized by PT in descending order of total frequency. The incidence of TEAEs coded as injection site reactions will be summarized by type of injection (primary or booster) and by arm.

At each level of summarization, a subject will be counted only once for each AE he/she experiences within that level.

Data listings of all AEs and SAEs will be provided. Adverse events presented in the listings will be those recorded from the first dose date through the end of follow-up.

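### Protocol 8.3.1 implies that ordinary expected reactions may stay off the AE form, in conflict with the all-AE rule in 8.4, 8.13 and 8.15; its fever entry also needs reconciling

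*Protocol*

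**What the plan says.** Protocol 8.3.1 lists expected events for GnRH therapy, bisphosphonates, GM-CSF and the vaccine. The vaccine list covers injection-site pain, redness, swelling, induration and pruritus, then systemic reactions beginning with fever of 104°F or more and ending: "myalgia, headache, nausea, fatigue lasting less than 72 hours are expected events for PROSTVAC-V/F".

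Two sentences on the AE form follow. The first opens "If, however, the investigator considers an expected event to be unexpectedly severe or more frequent than usual" and takes as its reference a prostate cancer patient treated with GnRH agents, GM-CSF or bisphosphonates. The second covers an event that is "associated with PROSTVAC-V/F, and is unexpectedly severe, such as a dose-limiting toxicity, it will also be recorded on the AE CRF".

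Protocol 8.4 states the general rule. Events reported by the subject, observed by the investigator or "documented in medical records will be listed on the AE CRF", whether or not they are thought related to the vaccine. Sections 8.13 and 8.15 repeat the duty to record all events.

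Protocol 9.7 makes the between-arm comparison of frequency and severity, regardless of attribution, the main safety focus. SAP 9.1.1 adds: "The incidence of TEAEs coded as injection site reactions will be summarized by type of injection (primary or booster) and by arm".

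**The concern.** The plan gives sites two recording instructions and does not say which prevails. The events on which they differ are the short-lived local and systemic reactions that protocol 1.6 expects most often. The safety tables need those events. If some sites record every reaction and others only the unexpectedly severe ones, the tabulated rates reflect site practice as well as tolerability. The protocol plans 250 to 300 centers, so there is ample room for divergent readings.

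The documents describe no diary or separate reactogenicity form. Events are sought by non-directive questioning (protocol 7.2 and 7.3), and the Schedule of Events has a single adverse-event row. As far as the documents show, a reaction left off the AE form does not reach the tables.

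**Working it through.** The plan states no figure on this point, so there is nothing to reproduce. The check is a comparison of the texts, followed by a bounded illustration.

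**Step 1. What each section sends to the AE form.**

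| Protocol section | Rule |
|---|---|
| 8.2 | Defines an AE. Its exclusions concern pre-existing conditions, preplanned hospitalizations and diagnostic procedures. Expectedness is not among them. |
| 8.3.1, background therapy and GM-CSF | Expected event captured if unexpectedly severe or more frequent than usual |
| 8.3.1, vaccine | Event recorded if unexpectedly severe, a DLT being one example; no frequency trigger |
| 8.4 | All AEs, related or not |
| 8.13 | All AEs, however detected |
| 8.15 | All untoward events; points to 8.2 for the definition and 8.4 for exceptions |

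**Step 2. Do the 8.3.1 sentences have a function if 8.4 governs?** If every AE is recorded, an unexpectedly severe expected event is recorded anyway, and both sentences are redundant. They change something only if an ordinary expected event may be left off. The contrastive opening points to that reading, although the text never states it.

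**Step 3. What is exposed.** Inputs: 400 subjects per arm (SAP 4.1.5), so 800 in the two vaccine arms; and the rates in protocol 1.6, namely injection-site reactions at 50% or more, and headache, fatigue, myalgia and nausea at 10% or more, mostly Grade 1-2. With full recording:

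- injection-site reactions: at least 800 × 0.50 = 400 subjects;
- each of the four systemic terms: at least 800 × 0.10 = 80 subjects.

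**Step 4. Illustration of loss.** Let *r* be the true rate, *f* the share of subjects at sites that follow 8.3.1, and *s* the share of reactions those sites would call unexpectedly severe. Then

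tabulated rate = *r* × [1 − *f*(1 − *s*)].

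The documents give neither *f* nor *s*. Assumed ranges: *f* from 10% to 50%, *s* from 0 to 50%.

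| *f* | *s* | *r* = 50% reads as | *r* = 10% reads as |
|---|---|---|---|
| 10% | 0 | 50 × 0.90 = 45% | 9% |
| 10% | 50% | 50 × 0.95 = 47.5% | 9.5% |
| 50% | 0 | 50 × 0.50 = 25% | 5% |
| 50% | 50% | 50 × 0.75 = 37.5% | 7.5% |

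If *f* and *s* are equal across arms, every between-arm difference shrinks by the same factor. If *s* differs by arm, the direction of the distortion is not fixed.

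**Step 5. The fever entry.** Section 8.3.1 lists fever of 104°F or more among expected vaccine reactions. Section 8.3.2 treats vaccine-related events as unexpected "with the exceptions for injection site and systemic reactions as noted above". Section 5.2.1 exempts from the DLT definition "Systemic injection reactions lasting < 72 hours: fever; myalgia, headache, nausea, fatigue", with no temperature. Section 1.5.1 lists fever without a temperature among the normal events after vaccinia vaccination. Taken literally, the example in 8.3.1 covers the higher fever and not the lower one, which fits poorly with the other two sections. Fever is not among the reactions given a frequency in 1.6, so this is separate from the counting question.

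**The case against.** The strongest defense is that 8.3 only defines expectedness, while the recording rule is in 8.4 and is repeated. Section 8.15 says where exceptions to documentation are found and does not name 8.3. No sentence says that other expected events are omitted. This stands to the extent that under-counting is a risk and not a fact. It does not remove the conflict, because the conditional sentences are then redundant and nothing tells a site to disregard them.

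Several stronger readings are tempting, and the documents do not support them:

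- **That 8.3.1 restricts recording in terms.** The restriction is implied by the opening of the first sentence; the word *only* does not appear.
- **That the frequency trigger governs vaccine reactions.** It is tied to GnRH, GM-CSF or bisphosphonate treatment.
- **That a Grade 3 reaction lasting 60 hours must be left off the form.** Section 5.2.1 does exempt such a reaction from the DLT definition, but a DLT is only an example in 8.3.1. Since most reactions are Grade 1-2, an investigator could well call this one unexpectedly severe and record it.
- **That a vaccine difference would be hidden.** The control is itself a fowlpox vector, and protocol 1.3 describes its injection-site reactions as generally indistinguishable from those of subcutaneous vaccinia. Omission would reach all blinded arms, and for local reactions there may be little difference to lose.
- **That a fever below 104°F is definitely classed as unexpected.** Section 8.3.1 also makes an event expected if it is in the Investigator's Brochure, package insert or consent form, and the temperature appears in a list of examples. Under 8.11 the sponsor determines the expectedness of SAEs from the Brochure, so this wording does not control expedited reporting.

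**Conclusion.** The inconsistency is real and in the current text. It is a drafting conflict in the recording rules, with a possible effect on the completeness and site-to-site consistency of common Grade 1-2 reactions in the safety tables. It does not touch the survival analysis.

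The size of the loss cannot be determined. The figures in step 4 depend on assumed values of *f* and *s* and show scale only. The conclusion also assumes that no instruction outside the documents, such as form-completion guidelines, already settles the matter.

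The fever wording is a separate and smaller point. Whether the entry is intended or a slip cannot be told from the documents, and the recording conflict stands either way.

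**What to change.** Delete the two conditional sentences on AE-form capture in 8.3.1. Alternatively, replace them with one statement: all AEs are recorded under 8.4 whether expected or not, and expectedness affects only classification for reporting. That statement has to be added, because 8.4 and 8.13 require all AEs but do not mention expectedness. Send a site memo to the same effect.

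Separately, the sponsor should reconcile the fever entry in 8.3.1 with 8.3.2, 5.2.1 and 1.5.1. No threshold is proposed here.

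The cost is protocol wording and the memo. The downside is more mild events to record at any site that had been omitting them. No endpoint, dose or sample size changes.

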8.3.2 Unexpected Events

Unexpected events are those considered unexpected when it varies in nature, intensity or frequency from the information provided in the current adverse event list, the Investigator's Brochure, the package insert or when it is not included the informed consent document as a potential risk. An event will be considered to be *unexpected* for GnRH agonist/antagonist, GM-CSF, or bisphosphonate therapy or a study procedure if it is not identified in the package insert, or is unexpectedly more severe or more frequent than events described in the package insert, or is related to PROSTVAC-V/F (with the exceptions for injection site and systemic reactions as noted above).

8.4 Collecting and Recording Adverse Events

The Investigator will monitor the occurrence of adverse event for each subject during the course of the study. All AEs (as defined above) reported by the subject, observed by the Investigator, or documented in medical records will be listed on the AE CRF, whether believed by the Investigator to be related or unrelated to the study vaccine.

All AEs must be reviewed, graded and causality determined by an Investigator listed on the form FDA 1572 at the research center reporting the event(s). Collection of adverse events begins at the time the subject signs informed consent and continues for 28 days following administration of the last dose of study medication.

Adverse event terms should be recorded concisely, using acceptable medical terms. When possible, a diagnosis (*i.e.*, disease or syndrome) rather than the component signs and symptoms should be recorded on the CRF (*e.g.*, congestive heart failure rather than dyspnea, rales, and cyanosis). However, signs and symptoms considered unrelated to syndromes or diseases are to be recorded as individual adverse events on the CRF (*e.g.*, if congestive heart failure and severe headache are observed at the same time, each event is to be recorded as an individual adverse event). Only abnormal laboratory values that result in clinical sequelae or require medication for treatment should be recorded as an adverse event. The adverse event should not be recorded as a procedure or clinical measurement (*i.e.*, a laboratory or vital sign). The underlying reason for the procedure or the abnormal clinical measurements, and, whenever possible, a diagnosis, should be recorded. The diagnosis should be recorded; not the individual lab test name.

Death is considered to be an outcome of an adverse event. The cause of death should be recorded on the AE CRF (*e.g.*, congestive heart failure with an outcome of death rather than the term "death").

8.4.1 Progression of Underlying Malignancy

It is anticipated that a proportion of subjects will experience disease progression. When clinical disease progression is identified, the clinical event which marks or identifies the disease progression should be reported as the adverse event term for standard AE reporting, including SAE reporting, per ICH definitions of AE and SAE as reviewed in [Section 8.2](#) and [Section 8.8](#) of this protocol, respectively.

For the purpose of this study, progression of underlying malignancy is not considered an (S)AE. Hospitalization, prolonged hospitalization, or death due solely to the progression of underlying malignancy will be captured on the AE CRF, but may NOT be reported as an SAE. Clinical symptoms of progression may be reported as AEs if they cannot be determined to be exclusively due to the progression, or if they do not fit the expected pattern of progression for prostate cancer.

Symptomatic deterioration may occur in the absence of radiographic evidence of tumor progression in some subjects. Alternatively, the disease progression may be so evident that the investigator may elect not to perform further assessments. In such cases, the determination of clinical progression is based on symptomatic deterioration. In these cases, efforts should be made to quantitatively document the progression of the underlying malignancy to the extent possible.

If there is any uncertainty about an adverse event being due to the progression of prostate cancer, it should be reported as an (S)AE.

8.4.2 Pregnancy of a Female Partner

For the purposes of this study, pregnancy of a female partner will be captured using a modified SAE report form, however; the event is not considered an SAE and will be reported to the appropriate regulatory authorities in the annual safety update. Partner pregnancies will be followed through the term of the pregnancy or pregnancy termination and the birth of the child after the female partner has signed the Pregnant Partner Informed Consent Form. Subjects and their partners will be counseled as to any possible known risks to either the partner or the child.

8.4.3 Accidental Transmission of Vaccinia Virus

Accidental transmission of vaccinia virus to a clinic staff member or a member of the subject's family or personal contacts must be reported to the Investigator as soon as possible, but no later than 24 hours after he/she becomes aware. The Investigator must notify an Infectious Disease Specialist in the [REDACTED] Pharmacovigilance Group (PVG) if there is a suspected serious vaccinia reaction as soon as possible, but no later than 24 hours after he/she becomes aware. The Investigator should contact the BNI study Medical Monitor if there are specific questions in regard to the potential vaccinia reaction. A swab of the suspected lesion may be obtained from the study subject for confirmatory testing prior to administration of VIG. The Investigator should refer to the Management Plan for Potential Serious Vaccinia Reaction for recognition, diagnosis and treatment of a rare potential serious vaccinia reaction. This plan also describes when VIG is indicated for use and administration procedures. For further information or for a

supply of VIG in the United States, contact the Centers for Disease Control at [contact]. For centers outside the United States, VIG suppliers (where known) are listed in the Study Instruction Manual. The Investigator should refer to the Management Plan for Potential Serious Vaccinia Reaction. If VIG treatment is warranted, the person receiving VIG must sign the Consent Form to Administer Vaccinia Immune Globulin (VIG) **PRIOR** to administration of VIG.

